3.1.4 Time windows

Analysis time windows for safety variables and efficacy will be based on scheduled visits/cycles of the schedule of activities for each phase (see Table 1, Table 2, Table 3 and Table 4 of the CSP).

Time windows will need defining for any presentations that summarize or list values by visit. This will be applicable for RECIST assessments, laboratory, vital signs and ECG parameters. The following conventions should apply, unless otherwise specified:

- The time windows should be exhaustive so that data recorded at any time point has the potential to be summarized. Inclusion within the time window should be based on the actual date and not the intended date of the visit.
- All unscheduled visit data should have the potential to be included in the summaries.

- The window for the visits following baseline will be constructed in such a way that the upper limit of the interval falls half way between the two visits (the lower limit of the first post-baseline visit will be Day 2). If an even number of days exists between two consecutive visits, then the upper limit will be taken as the midpoint value minus 1 day.

RECIST assessments with regards to target lesion tumor size will be windowed as well. Whenever TL tumor size data for the week XX (Note: or visit at which progression was documented if before week XX) is available then this should be used in the analysis. A windowing rule will be applied and will follow the protocol allowed visit window; therefore, any RECIST scan performed within +/- 1 week of the protocol scheduled visit will be used for that visit.

Appendix C shows detailed derivation rules for the visit windows assessment for RECIST (target lesions), clinical chemistry, hematology, coagulation, vital signs, urinalysis and ECG parameters. Additionally, the definition of study periods in Section 3.1.3 will be used to ensure that assessments will be mapped to applicable analysis visits only (i.e. an assessment prior to first administration of maintenance treatment will be mapped to CCI [REDACTED] but considered part of the induction phase).

- For summaries showing the maximum or minimum values during treatment, the maximum/minimum value recorded after date of first dose of investigational product. will be used (regardless of where it falls in an interval).
- Listings should display all values contributing to a time point for a subject.
- For visit based summaries
 - If there is more than one value per subject within a time window then the closest value to the scheduled visit date should be summarized, or the earlier, in the event the values are equidistant from the nominal visit date. The listings should highlight the value for the subject that contributed to the summary table, wherever feasible.

Note: in summaries of extreme values (i.e. maximum on treatment) all post baseline values collected are used including those collected at unscheduled visits regardless of whether or not the value is closest to the scheduled visit date.

- Summary statistics for mean, standard deviation, median, and range will be presented by visits until there are at least 3 subjects with evaluable data. A minimum of 12 cycles will be presented in any case.
- For summaries at a subject level, all values should be included, regardless of whether they appear in a corresponding visit based summary, when deriving a subject level statistic such as a maximum.

3.1.5 Imputation rules

In general, there is no imputation of missing data for efficacy analyses.

For RECIST, in case of partially missing target lesion (TL) measurements the results will be scaled up as detailed in section 3.1.6.1.

How to handle not quantifiable data in PK summaries is outlined in section 3.2.3.3.

Imputation of partial dates will be applied only for AEs onset/worsening/stop dates, concomitant medication stop dates, death dates, smoking history and date of first diagnosis.

Unless otherwise specified, imputed dates will not be used to derive durations of events or treatments. In the listings the data will appear as they are reported in the database.

Safety assessment values of the form of “< x” (i.e. below the lower limit of quantification) or > x (i.e. above the upper limit of quantification) will be imputed as “x” in the calculation of summary statistics but displayed as “< x” or “> x” in the listings. Note that 0 should not be used as an imputed value in case the endpoint requires a log transformation.

Imputation of adverse event onset date/adverse event worsening date

Missing onset/worsening dates will be imputed according to the following rules:

- Completely missing dates will not be imputed. AEs will be considered as treatment emergent in maintenance, unless there is evidence to the contrary.
- If day is missing assume 01-MMM-YYYY unless:
 - month and year are the same as the first administration of study intervention in induction phase, then assume first dose date in induction phase.
 - month and year are the same as the date of the first administration of study intervention in maintenance phase, then assume first dose date in maintenance phase.
- If day and month are missing, then assume 01-JAN-YYYY unless:
 - year is the same as first administration of study intervention in induction phase and is different to first administration of study intervention in maintenance phase, then assume first dose date in induction phase.
 - year is the same as both, the year of first administration of study intervention in induction phase and the year of first administration of study intervention in maintenance phase, then assume first dose date in maintenance.

After applying these rules, if the imputed AE onset date is after a complete or imputed AE end date (or date of death), the imputed onset date will be the same as the complete AE end date (or date of death).

Imputation of adverse event / concomitant medication stop date

Adverse event/concomitant medication stop dates will be imputed. It will be used to allow determination of prior or concomitant medications. The imputation of AE end date does not affect definition of treatment emergent, with the exception of cases when it is used for the imputation of the onset date.

Missing stop dates will be imputed according to the following rules:

- Completely missing dates will be not imputed. Medications will be considered to be concomitant for both periods, induction and maintenance, unless there is evidence to the contrary.
- If the day is missing: input day as the earlier of either the DCO or the last day of the month
- If the month is missing: input the day and month as the earlier of either the DCO or the last day of the year (31-DEC-YYYY).

After applying these rules, if the imputed AE or concomitant medication stop date is after the date of death, the imputed stop date will be the same as the date of death.

If the AE/concomitant medication is ongoing, the stop date will remain missing.

Imputation of date of death

If a subject is known to have died where only a partial death date is available, then the date of death will be imputed as the latest of the last date known to be alive + 1 from the database and the death date using the available information provided:

- For missing day only - using the 1st of the month
- For missing day and month - using the 1st of January

If there is evidence of death but the date is entirely missing, it will be treated as missing, i.e. censored at the last known alive date.

Imputation of date of substance usage start/stop date

Start dates are only applicable for current and former substance usage. Missing start dates will be imputed according to the following rules:

- Completely missing dates will be not imputed.
- For missing day only - using the 1st of the month
- For missing day and month - using the 1st of January

Stop dates are only applicable for former substance usage. Missing stop dates will be imputed according to the following rules:

- Completely missing dates will be not imputed.
- For missing day only - using the last day of the month
- For missing day and month - using the latest of screening date and 31st of December (screening date is used here to ensure substance usage is former)

Imputed dates will be used in the calculation of smoking history durations. Note: To allow the calculation of the years smoking for current substance usage, the screening date will be considered in the formula as the end date (see further details in Section 3.2.1.1).

Imputation of date of original diagnosis

Missing dates of first diagnosis will be imputed according to the following rules:

- Completely missing dates will be not imputed.
- For missing day only - using the 1st of the month
- For missing day and month - using the 1st of January

Imputed dates will be used in the calculation of time from original diagnosis to first administration of study intervention.

Missing data due to COVID-19

No sensitivity analyses are planned due to the COVID-19 pandemic.

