4.1.2.2.1 Results of the Safety Run-In

Treatment in the maintenance phase of the trial began in June 2021 and the SRC completed an initial assessment of the safety run-in cohort in September 2021. While no DLTs were experienced by the first six participants, one participant experienced an SAE of neutropenic sepsis with a fatal outcome and one participant experienced an SAE of febrile neutropenia with a fatal outcome during the second cycle of AZD2811 treatment (ie, CCI [REDACTED] Both SAEs were attributed to AZD2811 treatment by the investigators. Additional information about these events and the identified risk of sepsis has been added to the Investigator's Brochure.

Treatment with AZD2811, of new participants entering the maintenance phase, was put on hold while additional data analyses were conducted, and the following protocol amendments were proposed to ensure the safety of current and future participants:

- Maximum AZD2811 dose permitted will be CCI [REDACTED]; maintenance phase eligibility criteria must be confirmed prior to dosing the first cycle of AZD2811
- AZD2811 must not be administered if there is any suspicion of disease progression. Every effort should be made to schedule tumour evaluation scans within 1 week prior

to dosing with AZD2811; scan results **MUST be reviewed** prior to dosing to confirm the absence of disease progression.

- AZD2811 must not be administered if there is any suspicion of infection; consider (prophylactic) antibiotics for participants experiencing Grade 4 ANC or at a high risk of infection. If infection is suspected, work up should be performed to identify whether there is an infection.
- AZD2811 dose will be reduced if a patient experiences Grade 4 ANC, irrespective of time to recovery
- An additional safety visit on Day 12 of [CC1] has been introduced to identify low ANC earlier in the cycle (from Phase I experience, the nadir is expected between 10 to 15 days after AZD2811 dosing).

After implementation of the above recommendations in CSP v8.0, an additional safety run-in cohort will be assessed by the SRC according to Section 4.1.2.2.

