If a subject does not discontinue, does not withdraw consent, does not progress during the induction phase (tumor assessment at week 6 or with symptomatic PD) or does not die in the induction phase, subjects will be assessed for disease progression in week **[REDACTED]** which is used to confirm eligibility for maintenance therapy. Subjects who either progress or are not eligible for maintenance for other reasons will have the end date of induction phase at the date of the respective Response Evaluation Criteria in Solid Tumors (RECIST) v1.1 assessment. These subjects roll over into safety follow-up period.

Subjects who do not progress based on RECIST v1.1 or die, and are assessed to be eligible to continue into maintenance phase are considered to have the induction phase completed with end date one day before date of first study intervention in maintenance phase.

Maintenance period

Participants who have not progressed per RECIST v1.1 at the end of the induction phase and who meet maintenance phase eligibility criteria will continue into the maintenance phase of the trial and be treated with AZD2811 + durvalumab or durvalumab monotherapy as maintenance therapy. The maintenance phase starts when a subject receives the first administration of IP (AZD2811+durvalumab or durvalumab monotherapy) in the maintenance phase.

Assessments performed pre-dose on CCI [REDACTED] will be considered part of the induction phase unless based on the time collected indicates that the assessment occurred after the first dose in the maintenance phase. Assessments performed on day of dosing where time is not collected are assumed to have been done pre-dose. Maintenance phase end date is the date of end of last treatment during maintenance phase (maximum of end of treatment of AZD2811 and end of treatment of durvalumab). Subjects can discontinue from maintenance phase by withdrawal of consent, progression, death or if other discontinuation criteria are met. A subject who has been treated for a minimum of 2 years of maintenance treatment and continues to experience CR, PR, or SD, as demonstrated by radiographic measures, may be considered for treatment discontinuation.

Safety and survival follow-up period

Safety (concomitant medications and AEs/serious adverse events) will be followed up until 90 days after last dose. Start date of safety follow-up period is one day after end of treatment date in either induction or maintenance phase as per eCRF. The end date is

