3.2.3.4 Adverse Events

An adverse event (AE) is the development of any untoward medical occurrence in a subject or clinical study participant administered a medicinal product and which does not necessarily have a causal relationship with this treatment. The full definition of AEs and serious AEs (SAEs) can be found in the CSP Appendix B.

AEs and SAEs will be collected throughout the study, from date of informed consent until 90 days after the last dose of study intervention. Events will be defined as treatment emergent if they started after dosing or prior to dosing and worsen following study intervention. AEs which start in induction phase and subsequently worsen in maintenance phase will be defined as treatment emergent for both phases. AEs which start in induction phase and are ongoing, but not worsened, in maintenance phase, will be presented for induction phase only. For dosing days, AE start timing will be collected as well to identify pre- or post-dose AEs. AEs which start on Cycle 1 Day 1 but with start time before dosing are not considered treatment emergent. AEs which start/worsen on CCI [REDACTED] but with start time before dosing are considered as treatment emergent for induction phase only as long as they do not worsen in maintenance phase afterwards.

AEs with start or worsening date in safety follow-up period (within 90 days after the last dose of study intervention) will be presented along with AEs occurring in the phase from which the subject discontinued.

A flag will be created to indicate AEs which occur within the 90 days safety follow-up period but after initiation of the first subsequent therapy following discontinuation of study intervention.

The Medical Dictionary for Regulatory Activities (MedDRA) (using the latest or current MedDRA version) will be used to code the AEs. AEs will be graded according to the National Cancer Institute Common Terminology Criteria for AEs (CTCAE Version 5.0).

Maximum CTCAE grades on treatment overall and by phase will be derived.

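### SAP 3.1.5 has no exception for an AE onset known only by year when that year is the maintenance start year but not the induction start year, so such AEs default to induction, against the SAP's own convention

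*SAP*

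**What the plan says.** SAP 3.1.5 imputes partial AE onset and worsening dates in three tiers.

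- **Date wholly missing.** Nothing is imputed, and "AEs will be considered as treatment emergent in maintenance, unless there is evidence to the contrary".
- **Day missing.** The first of the month is used, with two exceptions. One is for the month of the first induction dose. The other applies when "month and year are the same as the date of the first administration of study intervention in maintenance phase", and then the first maintenance dose date is taken.
- **Day and month missing.** "If day and month are missing, then assume 01-JAN-YYYY unless" one of two exceptions applies. If the "year is the same as first administration of study intervention in induction phase and is different to first administration of study intervention" in maintenance, the first induction dose date is used. If the "year is the same as both, the year of first administration of study intervention in induction phase" and that of the first maintenance dose, the first maintenance dose date is used.

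Phase then follows from the date. Under SAP 3.1.3, patients who go on to maintenance are "considered to have the induction phase completed with end date one day before date of first study intervention in maintenance phase". SAP 3.2.3.4 adds that "AEs which start in induction phase and are ongoing, but not worsened, in maintenance phase, will be presented for induction phase only".

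SAP 4.2 lays out summaries by phase, with 'SoC' (which includes patients on durvalumab monotherapy in maintenance) beside 'AZD2811 + Durva'.

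**The concern.** The year-only tier lacks the mirror of its first exception. When the reported year is the maintenance start year and induction began the year before, neither exception applies and the onset becomes 1 January. That day falls after the first induction dose and before the first maintenance dose, so the AE lands in induction. The day-missing tier has the corresponding maintenance exception, and the SAP gives no reason for treating the year-only case differently.

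The proviso about worsening gives limited protection, because the same rules impute worsening dates. A worsening known only by that year is also set to 1 January.

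What is at stake is the phase in which an AE is displayed. The abbreviated CSR concentrates on safety, only 9 patients received the combination (Protocol 9.4), and the two treatment columns appear side by side within each phase. A rule that can lower maintenance counts in one column and not the other should be there by intent.

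**Working it through.** The plan states no figure on this point, so the check applies the written rule to the dates the documents allow.

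**Inputs**
- Earliest maintenance start: "Treatment in the maintenance phase of the trial began in June 2021" (Protocol 4.1.2.2.1), taken as 1 June 2021.
- Latest AZD2811 start: 14 December 2021 (Protocol 4.1).
- Last participant first dose: about five months before the 18 June 2022 data cut-off (SAP 3.1.1), so about 18 January 2022.
- Induction length: redacted. Assumed to be 4 cycles × 21 days = 84 days. Protocol Table 1 runs Cycles 1 to 4 and Table 3 starts at Cycle 5. Protocol 8.5.1 equates a 14-day delay with Day 35 of a maintenance cycle, and 35 − 14 = 21; the same cycle length is assumed for induction. Upper end of the range, allowing the 14-day delay of Protocol 8.2.4 four times: 84 + 4 × 14 = 140 days.

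**Step 1: one patient through every tier.** First induction dose 1 November 2021; first maintenance dose 84 days later, 24 January 2022.

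| Onset as reported | Imputed date | Phase |
|---|---|---|
| wholly missing | none | maintenance |
| January 2022 | 24 January 2022 | maintenance |
| 2022 | 1 January 2022 | induction |
| 2021 | 1 November 2021 | induction |

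The last row is right, since maintenance had not begun in 2021. The third row is out of line: knowing more (the month) or less (nothing) gives maintenance, but knowing only the year gives induction.

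**Step 2: does a later rule repair it?** The closing adjustment in SAP 3.1.5 resets an imputed onset that falls after the AE end date or death. It can only move the onset earlier, so it does not help.

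**Step 3: AZD2811 patients.** Their maintenance starts lie between 1 June and 14 December 2021, which is 197 possible days. Counting back from 1 June 2021, the earliest induction start is 9 March 2021 at 84 days and 12 January 2021 at 140 days. None of the 197 days gives different start years. A difference would need induction to begin by 31 December 2020, which is 152 days before 1 June 2021. A year-only 2021 onset therefore meets the shared-year exception and goes to maintenance. A year-only 2022 onset becomes 1 January 2022, which is already after their first maintenance dose.

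**Step 4: monotherapy patients.** At 84 days, induction starts from 10 October to 31 December 2021 lead to maintenance starts from 2 January to 25 March 2022, and the gap applies. At 140 days the windows are 15 August to 31 December 2021 and 2 January to 20 May 2022. Patients with both first doses in 2021, or both in 2022, are not affected.

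**Step 5: where might the true onset lie?** From 1 January to 18 June 2022 is 169 days. At 84 days of induction, between 168 and 86 of those days fall on or after the first maintenance dose, depending on start date (86/169 = 51%). At 140 days the last affected patient, starting maintenance on 20 May, has 12 + 18 = 30 of 169 (18%). The true phase is therefore uncertain, and how uncertain depends on the redacted length.

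**The case against.** The strongest reply is that the true phase of these AEs is unknown. An affected patient is still in induction from 1 January 2022 until the first maintenance dose. In the 24 January example that is 23 of 169 days (14%); for a 25 March start it is 83 of 169 (49%). A reader might infer that every such AE is misclassified. The documents do not support that: all are assigned to induction, and some of those assignments will be right. The amended rule is likewise a convention and would err in the other direction for some records.

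A reader might also infer that a treatment comparison is biased. None is planned. The study is single-arm, SAP 4 makes the analysis descriptive with no hypotheses, and the decision to stop enrolment was already taken on 14 December 2021. An informal reading across columns is possible, but no test or estimate rests on it.

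Nor does any AE drop out of the safety report. The imputed date is after the first induction dose, so the AE stays treatment-emergent and is counted in induction and in the combined summaries (SAP 4.2.3.2). Listings show dates as recorded.

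Finally, the affected set may be empty. Protocol 8.3.2 collects AE start dates, AEs are assessed at study visits, and data queries are raised, so an on-study onset with no month should be rare.

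All of this stands and limits the consequence. It does not explain why one tier departs from the convention of the others.

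**Conclusion.** The point holds as a gap in a stated rule with a minor consequence. Followed literally, SAP 3.1.5 assigns a year-only onset in the maintenance start year to induction when induction began the year before. The SAP sends the comparable ambiguous cases to maintenance: wholly missing dates, missing days in the maintenance start month, and a year shared by both phases.

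The restriction to one group rests on the June 2021 maintenance start, the 14 December 2021 limit on AZD2811 starts, and an interval from first induction dose to maintenance of no more than 151 days. On those terms no AZD2811 patient can be affected, and among monotherapy patients only those straddling 2021/2022 can be. The effect on the 'SoC' maintenance counts cannot be quantified, because the documents do not say how many year-only onsets exist.

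**What to change.** Add a third exception to the year-only rule in SAP 3.1.5: where the year is that of the first maintenance administration and differs from that of the first induction administration, assume the first maintenance dose date. In the worked example the onset moves from 1 January to 24 January 2022 and is counted in maintenance.

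The cost is one bullet in the SAP and one line of code. On the stated dates nothing changes for AZD2811 patients. The small downside is that some AEs that truly began in induction will be shown in maintenance, which the SAP's other rules for ambiguous dates already accept.

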3.2 Outcome variables

3.2.1 General variables

3.2.1.1 Demographics and baseline characteristic data

Demographics and baseline characteristics will be assessed at screening and/or on date of first administration of study intervention in induction phase (necessarily before first administration). For rescreened subjects, data re-entered at the re-screening visit will be used for analysis.

Demographic variables are age in years, sex, ethnicity, race and country. Following age groups will be created: age group 1: $\geq 18 - <50$, $\geq 50 - <65$, $\geq 65 - <75$, ≥ 75 and age group 2: $\geq 18 - <65$, ≥ 65 in years. Further subject characteristics include height in cm, weight in kg and body mass index (BMI) in kg/m^2 at baseline. Weight groups of <70 , $\geq 70 - <=90$, >90 in kg will be derived. The BMI is calculated as weight in kg divided by (height in m)². BMI groups of $<=25$, $>25 - <=30$, >30 kg/m^2 will be derived.

The BMI will be calculated considering the following formula $\text{BMI} (\text{kg}/\text{m}^2) = \text{weight} / (\text{height})^2$. To evaluate nicotine, use and consumption, number of pack years as number of pack-years = (number of packs / day) * numbers of years smoking will be calculated. Number of years smoking is calculated as (end date – start date +1)/365.25 (in case of missing or partial dates, imputed dates will be used for this calculation, see section 3.1.5). The end date for current substance usage will be the date of the screening (or re-screening) visit. If subject provides information on number of packs per week instead of per day, number of packs will be divided by 7 to be used in this formula.

Time (weeks) from original diagnosis to first administration in induction phase will be derived as

$$(\text{date of first administration in induction phase} - \text{date of original diagnosis} + 1)/7.$$

In case of missing date of original diagnosis, use imputed date instead, see section 3.1.5.

Subject recruitment will be also presented by region, country and center using the following regional groups: Asia (S. Korea), Europe (Spain, Poland) and North America (United States, Canada).

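### The year-only smoking stop date is imputed as the latest, not the earliest, of screening and 31 December, which overstates pack-years for former smokers

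*SAP*

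**What the plan says.** SAP section 3.1.5 restricts the rule to people already classed as former users: "Stop dates are only applicable for former substance usage". A stop date that is wholly missing is left missing. If the month and year are known, the instruction is "For missing day only - using the last day of the month". If only the year is known, it is "using the latest of screening date and 31st of December (screening date is used here to ensure substance usage is former").

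The section generally keeps imputed dates out of duration calculations unless stated otherwise, and smoking is a stated exception: "Imputed dates will be used in the calculation of smoking history durations". Section 3.2.1.1 then gives the formulas: "Number of years smoking is calculated as (end date – start date +1)/365.25" and "number of pack-years = (number of packs / day) * numbers of years smoking will be calculated". For current smokers, "The end date for current substance usage will be the date of the screening (or re-screening) visit".

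The result is reported in Table 14.1.8, the nicotine use summary for the Safety set.

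**The concern.** The parenthesis in the rule says that screening is there to keep the usage former. A cap does that, and a cap is the minimum of two dates. The rule as written takes the maximum, which makes screening a floor.

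Two neighbouring rules suggest a slip and not a choice. The stop-date rule for adverse events and concomitant medication in the same section has the expected form: "input the day and month as the earlier of either the DCO or the last day of the year (31-DEC-YYYY"). The missing-day smoking rule keeps the imputed date inside the recorded month. A stop recorded as December 1990 therefore becomes 31 December 1990, while a stop recorded only as 1990 becomes the screening date decades later.

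At stake is whether the reported pack-years are right. Protocol section 2.2 describes SCLC as strongly associated with tobacco smoking, so this is a relevant baseline characteristic. A program that follows the SAP to the letter would produce pack-years that contradict the stop year in the database.

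**Working it through.** The plan states no figure to reproduce, so the check applies its rule and formulas to dates.

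**Logic.** Let S be the screening date and Y the recorded stop year. The rule gives stop = max(S, 31 Dec Y), which is never before S.

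- Y earlier than the screening year: 31 Dec Y is before S, so stop = S. This is the end date of a current smoker, and Y has no influence.
- Y equal to the screening year: stop = 31 Dec Y, which is after S unless S is itself 31 December.

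As a check, every screening date in a two-year span from 1 September 2020 was paired with every stop year from 1960 to the screening year, 45,381 pairs in all. No imputed stop fell before screening, and 728 fell after it. That is one for each of the 730 screening dates except the two that are 31 December.

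**Size.** Illustrative inputs, assumed and not from the documents: start 1 January 1980, one pack a day, S = 15 June 2021. Years smoked = (end − start + 1)/365.25.

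- SAP rule, any stop year from 1990 to 2020: end = 15 June 2021, so 15,142/365.25 = 41.46.
- Earliest rule, stop year 1990: end = 31 December 1990, so 4,018/365.25 = 11.00.

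| Stop year | SAP rule (latest) | Earliest | Excess (pack-years) |
|---|---|---|---|
| 1990 | 41.46 | 11.00 | 30.46 |
| 1995 | 41.46 | 16.00 | 25.46 |
| 2000 | 41.46 | 21.00 | 20.45 |
| 2010 | 41.46 | 31.00 | 10.46 |
| 2020 | 41.46 | 41.00 | 0.45 |
| 2021 | 42.00 | 41.46 | 0.54 |

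For stop years before the screening year, the excess is the time from 31 December of the stop year to screening, multiplied by packs per day. For a stop in the screening year, it is the time from screening to 31 December, multiplied by packs per day. The ratio of the two results runs from 3.77 (1990) down to 1.01 (2020 and 2021).

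**Effect on a group mean.** Protocol section 9.4 gives 9 patients on AZD2811 plus durvalumab. If all nine contributed a value and one had the 1990 profile, the group mean would rise by 30.46/9 = 3.4 pack-years. With the 2020 profile it would rise by 0.45/9 = 0.05.

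**Missing-day rule.** The last day of the month can fall up to about 30 days after screening when the stop is in the screening month. That is 30/365.25 = 0.08 pack-years at one pack a day.

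**The case against.** The strongest reply concerns reach. Pack-years appear as a summary in one descriptive baseline table. The SAP plans no subgroup analyses (section 3.1.7) and no hypothesis tests (section 4), and efficacy data are listed only, so no conclusion about safety or efficacy turns on this. The rule touches only former smokers with a known year and no month or day. The documents do not say how many there are, and there is no basis in them for calling such dates common. All of this stands and limits the importance of the point.

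Three further replies stand in part:

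- Smoking status is not altered. The substance usage categories in Table 14.1.8 still separate former from current smokers. Only the duration and the pack-years lose the distinction.
- Listings show dates as reported, and a tobacco listing is planned (Appendix 16.2.4.2.6), so a reader could find the partial date. That does not correct the table.
- The values under the earliest rule are not the true values. They are the upper end of what the recorded year allows, so up to about one year of overstatement can remain.

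Protocol Table 1 mentions collecting smoking pack-years at screening, which might seem to make the derivation unnecessary. However, SAP section 3.2.1.1 derives them from dates, so the rule takes effect as written.

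**Conclusion.** The rule is wrong as written. It cannot place a stop date before screening, it contradicts its own stated reason, and it gives former smokers with a year-only stop date the smoking duration of a current smoker or slightly more. Compared with the earliest rule, the excess in the example runs from about half a pack-year for a stop close to screening to about 30 for a stop in 1990. It scales with packs per day. These sizes rest on the assumed start date, screening date and consumption, but the direction of the error does not. The consequence is confined to the pack-years derived for Table 14.1.8. It should be corrected because the reported number would be wrong and nothing is gained by keeping the rule.

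**What to change.** In SAP section 3.1.5, under substance usage stop dates with day and month missing, replace *latest* with *earliest*, so that the imputed stop is the earlier of the screening date and 31 December of the recorded year. Apply the same cap to the missing-day rule: the earlier of the screening date and the last day of the recorded month. For rescreened subjects, use the same screening or re-screening date that section 3.2.1.1 uses for current smokers.

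The cost is one word for the main correction, a short phrase for the cap, and about one line of code for each. No new data are needed and no other analysis changes.
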